7.0 Study Medication

7.1 Fisetin

Fisetin (FIS) is widely available as a dietary supplement. To our knowledge, FIS has not been withdrawn from any market globally.

FIS (3,3',4',7-tetrahydroxyflavone) is a member of the flavonoid family, a family of naturally occurring polyphenolic compounds. FIS, a high Trolox-equivalent antioxidant, is present in low concentrations in many fruits and vegetables, such as apples, persimmon, grapes, onions, and cucumbers, with the highest concentration found in strawberries (160 μ g/g)²⁷⁻²⁹. Fisetin capsules supplied are to be opaque blue in color.

7.2 Placebo Control

The placebo comparator used for this study is to be manufactured using the same size #3 opaque blue capsule. Each placebo capsule is mainly composed of cellulose along with some coloring agents to approximate the appearance of the active capsule.

7.3 Supply

While Fisetin (FIS) is currently available and marketed as a dietary supplement, this study will use a product manufactured under cGMP conditions. The FIS will be supplied in 100 mg capsules to be administered orally. Both Fisetin and Placebo will be obtained from Vital Nutrients, a contracted GMP manufacturer.

Vital Nutrients
[name]
[name]

Vital Nutrients will ship Study Medication directly to the Vail Health Hospital Pharmacy within Vail Health Hospital. All subjects will obtain their Study Medication directly from Vail Health Hospital Pharmacy.

Methods for ordering, dispensing and tracking Study Medication shipments are outlined in specific Standard Operating Procedures maintained by the Vail Health Hospital Pharmacy.

7.4 Administration of Study Medication

7.4.1 Route and Dosage

Fisetin (FIS) 100 mg capsules (~20 mg/ kg/ day) will be administered orally for two consecutive days (days 1 and 2) followed by 28 days off. A second course will be given for two consecutive days (days 31 and 32)

Placebo (visually identical) will be taken orally using the same dosing schedule described for FIS. Number of capsules per day will be the same number as if receiving FIS.

There are no recommended dosing adjustments for kidney or liver dysfunction.

Subjects will be instructed to complete dosing in as short of a time as possible, with a goal of 10 minutes and a maximum time of 60 minutes to complete ingestion of the capsules. They will further be instructed not to increase medication dosing should a particular dose be missed.

7.4.2 Rationale for FIS Dose and Intermittent Dosing Schedule

7.4.3 Dose

We previously treated 4 male and 4 female 8-month-old C57/Bl6 mice with FIS 500 mg/kg/day, (a dose 25-fold higher than the dose to be used in this clinical trial) by oral gavage for two consecutive days and compared study endpoints to four male and four female mice treated with control. We found no evidence of substantial toxicity, as assessed by monitoring activity, food intake, and respiratory quotient in metabolic cages (Comprehensive Laboratory Animal Monitoring System, Columbus Instruments) for 48 hours after the last FIS dose.

In addition, we administered 100 mg/kg/day for 2 consecutive days by mouth (a dose five times the dose proposed in in this clinical trial) to two older Rhesus monkeys, ages 18 and 28 years. Because these animals are considered elderly for their species it would be expected that they be more vulnerable to adverse events. In over one month of close monitoring, neither monkey showed evidence of debilitation, including reduced appetite, altered activity, vomiting, or diarrhea.

Finally, others have treated mice with FIS 50 mg/kg/day for weeks without evidence of toxicity³⁰.

Based on this data and considering the high rate of drug metabolism in mice compared to humans and differences in physiology between non-human primates and humans, we believe that a daily dose of ~20 mg/kg/day is a safe dosage at which to complete this early stage clinical study. In addition, this smaller dose serves to minimize excessive pill burden for study subjects.

7.4.4 Intermittent Dosing Schedule

Senolytic drugs (including FIS) can effectively kill senescent cells with one to two doses given systemically¹. We believe that allowing two week breaks between dosing will be more tolerable to patients as compared to sustained dosing, therefore minimizing protocol deviations.

We further believe that intermittent dosing may minimize the occurrence of potential drug-drug interactions and hopefully decreasing the frequency or magnitude of any potential side effects further discussed in **Section 13.1** of this protocol.

7.4.5 2 Month Duration

We have chosen a 2-month (32 days) dose duration based upon pre-clinical studies reviewed in **Section 5.3** of this protocol. Several studies have treated mice with our proposed dose and more, for over two months (equivalent of ~20 years in the human lifespan). Considering the comparative life span between the mouse model and of humans, we believe that a 2-month duration is a safe and effective length of time.

7.4.6 Human Evidence of Safe Dosing

As discussed in Section 5.4 there appears to be no serious safety barriers to administration of Fisetin at the proposed dosage.

7.5 Study Design and Duration

7.5.1 Study Design

This is a prospective, randomized, placebo controlled, double blind study to be conducted at the Steadman Clinic and the Steadman Philippon Research. A total of no more than 100 will be randomized 1:1 to receive either Fisetin (FIS) or placebo.

7.5.2 Study Duration

When every treated subject has reached 18 months following treatment, the study will be considered complete, and the data will be summarized. It is estimated that enrollment will take approximately 18 months. Each study subject will be followed for 12 months, which will be considered the final visit. The PROs will be administered electronically at 18 months. The total duration of Study is approximately 36 months. An additional 4 months will be spent closing the study database and in data analysis.

The proposed start date is December 1, 2019, with anticipated last visit September 1, 2022.

8.0 Study Objectives and Endpoints

8.1 Objectives

8.1.1 Primary Objective

To evaluate as compared to placebo:

1. The safety of administering Fisetin (FIS) in subjects with osteoarthritis (OA).

8.1.2 Secondary Objectives

To evaluate as compared to placebo:

1. Reduction of pro-inflammatory and cartilage degenerating SASP markers;
2. Improvement in physical function of the target knee;
3. Improvement in PROs;
4. Improvement in the quality of articular cartilage in the knee joint;
5. Reduction in time to conversion to alternative treatment.

8.2 Study Endpoints

8.2.1 Primary Endpoint:

1. Occurrence of adverse events.

8.2.2 Secondary Endpoints

Statistically significant as compared to placebo:

1. Improvement in serum measures of inflammation and cartilage degenerating SASP markers;
2. Improvement in lower-extremity kinematic testing with video-motion analysis; isokinetic dynamometry testing, functional performance testing, ROM;
3. Improvement in IKDC, Lysholm, TEGNER, WOMAC and SF-12 surveys;
4. Improvement in the quality of articular cartilage in the knee joint as measured by T2 and T1rho relaxometry;
5. Days from day one of Study Medication intake to conversion to alternative therapy.

Additionally, we will review and discuss any possible correlation among secondary endpoint results.

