9.1 Enrollment Criteria

9.1.1 Inclusion Criteria

Subjects will be included if all of the following criteria are met:

1. Are male or female, ages 40-80;
2. Are willing to comply with all study related procedures and assessments;
3. Are ambulatory as defined by ability to complete functional performance testing;
4. Radiographic evidence of Kellgren-Lawrence grade II-IV osteoarthritis in one or both knees;
5. Scores 4-10 on the Numerical Rating Scale (NRS) for pain;
6. Stable dose of screening/baseline medications for at least 2 months prior to the anticipated date of study drug dosing.

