11.6.2 Quantitative Magnetic Resonance Imaging (MRI): (Visits 2, 5, 6)

Quantitative MRI will be performed at the Steadman clinic. In preparation for MRI, subjects will be asked to remove their shoes and any metal that may interfere with the scan (e.g. metallic clothing, jewelry) and will be provided with disposable, MRI-compatible clothing if needed.

Images will be acquired on a 3T Siemens Magnetom Skyra-fit scanner.

For the screening and follow-up MR scans, morphological T1 MR images will be acquired. These images provide evaluation of knee structure. It is well known that structural alteration can lead to loss of collagen organization (e.g., torn fibers and scar tissue) and changes in water content (e.g., dehydration).

In addition, quantitative T2 MR images, which provide data on tissue MR signal relaxometry values, will be acquired to provide information regarding cartilage health including the relative level of water and collagen organization within the tissue.

A Study Team member will physically collect the hard drive and will transfer MR images to the SPRI Imaging Research network drive, accessible only to specific SPRI personnel via password protected accounts. The images will also be uploaded to the secure TSC PACS (Picture Archiving And Communication System) for radiological assessment by a blinded radiologist. Objective morphological measurements and Quantitative MRI value analysis will be performed from the DICOM files using Mimics, ImageJ, 3D Slicer, and MATLAB. Specifically, the regions of interest will be segmented in either Mimics or 3D Slicer (equivalent function software) and the masks will be exported to BPM format (bitmap) and imported into MATLAB for extraction of T2 or T2 values within the regions of interest. Morphological measurements may be taken in either Mimics, ImageJ, or 3D Slicer depending upon software scheduling coordination. All of these programs perform equivalently for this purpose. Results will be output to an Excel spreadsheet for statistical analysis.

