15.5.2 Secondary Endpoints

15.5.2.1 Imaging Assessment of OA

Quantitative MRI will be performed at baseline and at 6 months and 12 months after initiation of medication. T2 and T1rho relaxometry will be performed. Linear mixed-effects modeling with random intercepts will be used to appropriately match the repeated measures design. A group-by-time interaction will be modeled to investigate both early improvement in tissue quality and maintenance of such an effect to 12 months as well.

Secondarily, multivariable modeling techniques such as support vector machines (SVM) and/or principal components analysis (PCA) will be pursued to characterize the SASP response profile that distinguishes the FIS and placebo groups.

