15.6 Statistical Power and Sample Size

Anticipated effect sizes for the group difference with respect to MRI-assessed cartilage quality were derived from the literature, however a paucity of literature was found in the knee OA literature when comparing various grades of advanced osteoarthritis. As a simplifying assumption, we derived an anticipated effect size for clinically meaningful change in T1rho values from a recent meta-analysis (MacKay, et al, 2018, J Osteoarthritis and Cartilage) that reported the standardized mean difference (SMD) between mild OA and healthy controls.

We aim to power this study to detect an effect size between the FIS and placebo treatment groups that is equal to the meta-analyzed effect size described above (SDM=0.73). The statistical method for this unadjusted, independent groups comparison of means, and the significance level will be set at $\alpha=0.05$. Assuming 2-tailed testing and requiring 80% statistical power, 30 patients per group are sufficient to detect the effect size of interest. Anticipating a 20% drop-out or incomplete follow-up rate, we aim to enroll no more than 100 total OA patients (30 per groups, and 6 per group to account for 20% drop out). Power calculations were performed using G*Power (version 3.1; Universität Düsseldorf).

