15.7 Missing Data

Whenever possible, statistical methods such as linear mixed-effects modeling which naturally handle missing data will be utilized. Missing data will be investigated carefully by the biostatistician, the study manager and the clinical staff to assess its probable cause, and whether missing not at random (MNAR, missingness dependent on outcome), missing at random (MAR, missingness not dependent

on outcome but can be fully accounted for by other non-missing covariates) or missing completely at random (MCAR, missingness independent of both observed variables and unobserved parameters of interest) is most likely.

If any missing data patterns are determined to be MNAR, this observance will be reported narratively in the final report(s) and publication(s), and no imputation methods will be pursued. Little's test will be used to assess whether missing values are missing completely at random (MCAR). For methods that require complete data or listwise deletion (e.g. PCA), and where missing data is determined to be reasonably missing at random (MAR or MCAR), multiple imputation using predictive mean matching will be employed.

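### Grade IV knees are eligible, but the T2/T1rho endpoint has no rule for absent or lost cartilage, so cartilage loss does not count as worsening

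*Combined protocol and SAP*

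**What the plan says.** The cartilage endpoint, item 4 of section 8.2.2, is "Improvement in the quality of articular cartilage in the knee joint as measured by T2 and T1rho relaxometry". Inclusion item 4 in section 9.1.1 reads "Radiographic evidence of Kellgren-Lawrence grade II-IV osteoarthritis in one or both knees". The MRI exclusion (9.1.2, item 8) concerns body size, metal, devices and claustrophobia. No criterion refers to remaining cartilage, and grade IV is neither capped nor stratified.

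On measurement, section 11.6.2 says that "the regions of interest will be segmented in either Mimics or 3D Slicer" and takes relaxation values inside the resulting masks. It also says "Objective morphological measurements and Quantitative MRI value analysis will be performed from the DICOM files", with results sent to a spreadsheet for statistics. It does not list the regions, say whether they stay the same across visits, or say how a region without cartilage is recorded.

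On analysis, section 15.5.2.1 says "Quantitative MRI will be performed at baseline and at 6 months and 12 months after initiation of medication" and "Linear mixed-effects modeling with random intercepts will be used to appropriately match the repeated measures design", with a treatment-by-time interaction. Under section 15.7, data judged missing not at random are described in the reports, "and no imputation methods will be pursued".

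On size, section 15.6 takes a standardized mean difference of 0.73 in T1rho, from mild OA against healthy controls, and concludes that "30 patients per group are sufficient to detect the effect size of interest". It adds 6 per group for 20% loss, under a ceiling of 100 in total.

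**The concern.** A relaxation time is a property of tissue that is present. With grade IV knees eligible, some regions may have no cartilage at baseline and others may lose it by month 6 or 12. Where a region is bare, there is no value. Where part of it is lost, the value is a mean over different, surviving tissue. In both cases the worst structural outcome leaves the endpoint instead of counting against the arm in which it happened.

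The trial's title is about attenuating cartilage degeneration, so preserving cartilage is the effect sought. If loss differed by arm, a T2/T1rho difference in either direction could not be separated from the loss itself. More loss on placebo could hide a benefit; more loss on fisetin could mimic one. The number with a usable T1rho value may also fall below the number retained, and section 15.6 treats the two as the same.

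**Working it through.** **1. The plan's own figure.** Inputs from 15.6: SMD 0.73, two-sided alpha 0.05, power 80%, two independent means; allocation is 1:1 (15.2). Normal approximation: n = 2 × (1.960 + 0.842)² / 0.73² = 15.70 / 0.533 = 29.5, so 30 per group. The noncentral t gives 30.45, so 31, with 79.4% power at 30. The stated 30 reproduces and is not in dispute.

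**2. Does existing text cover absent or lost cartilage?**
- *Partial loss.* The mask shrinks and a mean is still recorded. Nothing is flagged as missing, so 15.7 is not triggered, and the mixed model takes the value as it stands.
- *Complete loss of a region.* The value is missing because of the outcome. A random-intercepts model does not correct that, and 15.7 then allows only a narrative account.
- *Conversion to surgery.* Under 15.5.2.4 these subjects are removed, so some of the worst structural courses may leave the data as well.
- *Morphology.* Measurements are taken and exported (11.6.2), but section 15 names no morphological endpoint or model.

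**3. Size of the survivor effect (assumed inputs).** Let values within a knee be normal with SD 1, with no true change in the remaining tissue, and let a share q of cartilage be lost. If the highest-valued tissue goes first, the mean shifts by −φ(z)/(1 − q), where z is the 1 − q normal quantile. If loss correlates only r with the value, multiply by r.

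| Share lost q | φ(z) | Shift, r = 1 | Shift, r = 0.5 |
|---|---|---|---|
| 5% | 0.103 | −0.11 | −0.05 |
| 10% | 0.175 | −0.195 | −0.10 |
| 20% | 0.280 | −0.35 | −0.18 |

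Units are within-knee SD. Equal loss in both arms largely cancels. With 10% lost in one arm and 5% in the other, the difference is 0.195 − 0.109 = 0.09 within-knee SD at r = 1. This scale is not that of the 0.73, which is standardized differently, and the documents give nothing to convert between them.

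**4. Power by scorable number (assumed shares).** The plan can be read two ways on enrolment. Section 6 gives 36 per arm, and 15.6 builds 36 from 30 evaluable. The synopsis gives 100 in total, which leaves 50 × 0.8 = 40 per arm after 20% loss. Noncentral-t power at SMD 0.73, two-sided 0.05:

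| Unscorable | From 30 per arm: n, power | From 40 per arm: n, power |
|---|---|---|
| 0% | 30, 79% | 40, 90% |
| 10% | 27, 75% | 36, 86% |
| 20% | 24, 70% | 32, 82% |
| 30% | 21, 64% | 28, 77% |
| 40% | 18, 57% | 24, 70% |

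This table removes whole subjects. It applies only if the analysed measure is missing for that subject. For any one knee measure, the power loss in step 4 and the averaging in step 3 are alternatives: the value is either absent or taken over the remainder.

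**The case against.** The strongest reply is that this is a regional matter on a secondary endpoint whose size nobody can state. Much of that stands.

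- A reader might infer that grade IV knees cannot be scored. The documents do not say how much cartilage such knees keep, and a knee with one bare region can still give values elsewhere.
- A reader might infer that the trial is underpowered for T1rho. At 40 per arm, power stays above 80% with 20% unscorable. The 20% allowance in 15.6 already includes incomplete follow-up, although it does not mention knees that were scanned but cannot be scored.
- A reader might infer that a drug preserving cartilage would look worse than placebo. That needs unequal loss, loss selective for high values, and little real effect on the remaining tissue. The documents give no 12-month loss rate, no order of loss and no direction of improvement for T2 or T1rho.
- A reader might infer that the morphological data go unanalysed. Section 11.6.2 exports them for statistics; what is absent is a named endpoint or model in section 15.
- Section 11.6.2 provides a blinded radiologist's assessment, and 15.7 requires missingness to be investigated. Neither enters the T2/T1rho comparison as a worsening.

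None of this supplies a rule for absent or lost cartilage.

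**Conclusion.** The gap is real. With grade IV eligible and values drawn only from segmented tissue, the analysis in 15.5.2.1 can record a mean over a shrinking region and never count cartilage loss as worsening. The mixed model and section 15.7 do not repair this.

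Its size is unknown. The shifts of 0.11 to 0.35 within-knee SD assume that 5 to 20% of cartilage is lost and that the highest values go first; they roughly halve at a correlation of 0.5. Bias between arms further requires loss that differs by arm. The power range of 75 to 57% from 30 per arm, or 86 to 70% from 40, rests on assumed unscorable shares of 10 to 40% of subjects. These figures illustrate; they do not forecast.

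The primary endpoint, adverse events, is untouched. The point still deserves action, because the trial is sized on this measure and the correction is cheap.

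**What to change.** In section 15.5.2.1:

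1. Define the scorable regions from the baseline scan alone, by readers blinded to follow-up images and to group, and keep them fixed at months 6 and 12. Setting them merely before unblinding is too late, because blinding lasts until the analysis is done and the follow-up scans would already exist.
2. Report and model regional cartilage volume or thickness alongside T2/T1rho, from the segmentations already made or from the morphological images where the sequence supports it. Partial or full loss then counts as worsening. State that a relaxometry improvement is not read as benefit where volume fell. This is the item that deals with partial loss; items 1 and 3 do not.
3. As a sensitivity analysis, give the worst rank to a baseline-scorable region that has lost all its cartilage.

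In section 15.6, state that 30 per group means subjects with a scorable T1rho value, and show power over an assumed unscorable range for both enrolment readings, as in the table above, without enrolling more.

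The cost is plan wording, a little more analysis of images already collected, and a less favourable stated power.

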9.0 Study Population

Male and female patients who present to the clinical practices of the Principal Investigator or Sub-Investigators will be enrolled if they meet all eligibility criteria. Subjects from the community who self-identify in response to a flyer, newspaper advertisement, or website will be enrolled if they meet all eligibility criteria.

9.1 Enrollment Criteria

9.1.1 Inclusion Criteria

Subjects will be included if all of the following criteria are met:

1. Are male or female, ages 40-80;
2. Are willing to comply with all study related procedures and assessments;
3. Are ambulatory as defined by ability to complete functional performance testing;
4. Radiographic evidence of Kellgren-Lawrence grade II-IV osteoarthritis in one or both knees;
5. Scores 4-10 on the Numerical Rating Scale (NRS) for pain;
6. Stable dose of screening/baseline medications for at least 2 months prior to the anticipated date of study drug dosing.

9.1.2 Exclusion Criteria

Subjects will be excluded if any of the following criteria are met:

1. Females who are nursing, pregnant or planning to become pregnant during the duration of study drug dosing;
2. Males who do not wish to abstain from sex or use contraceptive protection during study drug dosing and for 2 weeks after the last dose;
3. Subjects who do not have the capacity to consent themselves;
4. Subjects who are unable to tolerate oral medication;
5. Subjects having previously undergone any of the following treatments in the stated time window:
 - a. Surgery on the Study Knee in the past 6 months;
 - b. Partial or complete joint replacement in the study knee. Partial or complete joint replacement in the contralateral knee is acceptable as long as the surgery was performed at least 6 months prior to enrollment and the operative knee is asymptomatic;

-
- c. Patients who have undergone arthroscopic surgery (including microfracture and meniscectomy) on the Study Knee in the last 2 years prior to the Screening visit or are anticipated to have arthroscopic surgery on either knee at any time during the study period;
 - d. Steroid injection, including extended-release corticosteroid (e.g., Zilretta®) within the last 5 months;
 - e. Biologic (platelet-rich plasma, bone marrow, adipose tissue/cells) or hyaluronic acid injection into the Study Knee in the past 6 months;
6. Subjects with any of the following drug/medication statuses:
- a. Currently taking Losartan;
 - b. Opioid analgesics taken in the past 8 weeks and are not willing to discontinue these medications through the duration of the study;
 - c. Senolytic agents taken within the past 6 months and are not willing to discontinue these medications through the duration of the study, including: Fisetin, Quercetin, Luteolin, Dasatinib, Piperlongumine, or Navitoclax;
 - d. Drugs that induce significant cellular stress and are not willing to discontinue these medications through the duration of the study, including alkylating agents, anthracyclines, platins, other chemotherapy drugs;
 - e. **Subjects taking the following other drugs if they cannot be held (per the Principal Investigator) for at least 2 days before and during administration of Fisetin:** cyclosporine, tacrolimus, repaglinide, and bosentan.;
7. Subjects with any of the following disease statuses:
- a. Significant liver disease (i.e. greater than or equal to 2x the upper limit of normal bilirubin levels) or as in the opinion of the Principal Investigator;
 - b. Significant renal disease (eGFR of <60 ml/min/1.73m²) or as in the opinion of the Principal Investigator;
 - c. History of other formally diagnosed joint diseases including, osteonecrosis, acromegaly, Paget's disease, Ehlers-Danlos Syndrome, Gaucher's disease, Cushing's syndrome, Stickler's syndrome, joint infection, hemophilia, hemochromatosis, or neuropathic arthropathy of any cause;
 - d. Any active systemic autoimmune disease with musculoskeletal involvement or any history of systemic inflammatory arthritis;
 - e. Patients with type 1 or 2 diabetes (HbA1c \geq 6.5%) and/or taking medications that affect insulin levels, including: Metformin (within the last week), Glucocorticoids (within the last month), Acarbose (within the last week);

-
8. Subjects unable to safely practically undergo an MRI (BMI > 40 kg/m²) or size exceeding limits of MRI equipment, implanted metal in study knee near joint surface, incompatible implant/device, severe claustrophobia;
 9. Subjects that have any medical condition, including laboratory findings and findings in the medical history or in the pre-study assessments, that in the opinion of the Investigator constitutes a risk or contraindication for participation in the study or that could interfere with the study objectives, conduct or evaluation or prevent the patient from fully participating in all aspects of the study.

